#### **7.2.3.5. IP Dispensing and Instructions**

Each subject will receive a starter kit for the randomly assigned product cell (see section 6). Additional auxiliary product will also be dispensed, as needed. The site designee will review the treatment period instructions (Appendix VII) with the subjects. If Visit 2 is split into sub-visits, subjects will be instructed to begin following the treatment period instructions only after completion of the final Visit 2 sub-visit.

#### **7.2.3.6. AE Collection**

Subjects will be questioned and assessed for AEs before leaving the facility.

#### **7.2.4. Visit 3 (Week 1), Visit 4 (Week 4), & Visit 5 (Week 12)**

On the day of each study visit, subjects should remove all leave-on facial products (including eye makeup) and wash with the provided facial cleanser prior to the visit. No other topical products should be applied to the face until the study visit has been completed. Note: if a subject does not follow these directions, she will be asked to remove her facial products and wash her face with the auxiliary cleanser on-site prior to the acclimation period (Note: this will not be considered a deviation).

At each visit:

- Subjects will be interviewed for compliance with study instructions. This may occur during the acclimation period.
- Subjects will acclimate to conditions in the test facility for at least 15 minutes before the clinical and subjective evaluations of efficacy [REDACTED] are conducted.
- The clinical evaluations of efficacy [REDACTED] will be repeated as described in section 7.2.3.3.
- [REDACTED]
- [REDACTED]
- A trained site designee will review each subject's daily diary and inspect the IPs/auxiliary products to assess subject compliance (see section 7.3).
- Additional auxiliary products will be dispensed, as needed. Used Mask Activators and used auxiliary products will be collected and retained by study staff at the Site's discretion.
- Visit 4 only: An IP refill kit will be dispensed.
- Visit 5 only: all IPs will be collected and retained by study staff. Additional auxiliary product will be dispensed to subjects with instructions for the regression phase of the study (Appendix X). If Visit 5 is split into sub-visits, this will be completed at the final Visit 5 sub-visit.
- Subjects will be questioned and assessed for AEs and any changes in their health or concomitant medications.

#### **7.2.5. Visit 6 (Week 24)**

On the day of the study visit, subjects should remove all leave-on facial products (including eye makeup) and wash with the provided facial cleanser prior to the visit. No other topical products should be applied to the face until the study visit has been completed. Note: if a subject does not follow these directions,

she will be asked to remove her facial products and wash her face with the auxiliary cleanser on-site prior to the acclimation period (Note: this will not be considered a deviation).

At the visit:

- Subjects will be interviewed for compliance with study instructions. This may occur during the acclimation period.
- Subjects will acclimate to conditions in the test facility for at least 15 minutes before the clinical and subjective evaluations of efficacy [REDACTED] are conducted.
- The clinical evaluations of efficacy [REDACTED] will be repeated as described in section 7.2.3.3.
- [REDACTED]
- [REDACTED]
- A trained site designee will review each subject's daily diary and inspect the auxiliary products to assess subject compliance (see section 7.3).
- The daily diary and all auxiliary products will be collected and retained by study staff. If Visit 6 is split into sub-visits, this will be completed at the final Visit 6 sub-visit.
- Subjects will be questioned and assessed for AEs and any changes in their health or concomitant medications.

### 7.3. SUBJECT COMPLIANCE METRICS

IP/auxiliary product review, daily diary, and subject interview will be used to assess subject compliance. The AM & PM Cleanser and AM Moisturizer will not be weighed but should be visually assessed for usage compliance. Each Mask Activator supplied to the subjects should be reviewed by study staff for usage compliance and the remaining number of treatments will be recorded; the counter on each Mask Activator allows for 5 treatment-sessions and will reduce by 1 with each use.

The diary and Mask Activator must indicate at least 90% compliance (i.e. 3 usage misses in 30 days is allowed); anything less than that will be documented as a compliance deviation and the subject will be re-instructed on proper product usage or be dropped from the study at the PI's or designee's discretion after consultation with the Sponsor.

[REDACTED]

[REDACTED]

[REDACTED]

[REDACTED]

[REDACTED]

- [REDACTED]
- [REDACTED]

[REDACTED]

- [REDACTED]
- [REDACTED]
- [REDACTED]
- [REDACTED]
- [REDACTED]
- [REDACTED]

[REDACTED]

## 7.5. SUBJECT COMPLETION/WITHDRAWAL

### 7.5.1. Subject Completion

Subjects are considered to have completed the study when all study procedures have been completed as designated by the protocol. Completion should be noted on the Screening and Enrollment Log (or equivalent) as well as in the EDC system on the Subject Disposition page.

### 7.5.2. Subject Discontinuation

When an individual who has signed the ICD is not included in the study or discontinues/is discontinued prior to completing the study, the reason is to be documented on the Screening and Enrollment Log (or equivalent) and (only for randomized subjects plus screen failed subjects with a reported AE) in the EDC system on the Subject Disposition page. The subject disposition should also be summarized in the final study report. Reasons for subject discontinuation may include:

- Screen Failure (i.e. fails to meet inclusion/exclusion criteria or chooses not to participate)
- Participant is determined to be ineligible after enrollment
- Withdrawal by subject
- Non-compliance with study treatment (including non-compliance with product use/study directions)
- Lack of efficacy
- Protocol deviation/violation (other than non-compliance)
- Death (must be reported in accordance with the reporting requirements defined in the SAE section)
- Other AE/Serious AE (must be reported in accordance with the reporting requirements defined in section 10.3.3)
- Pregnancy (must be reported in accordance with the reporting requirements defined in section 10.3.5)
- Study terminated by Sponsor
- Lost to follow-up
- Other

Subjects may withdraw from the trial at any time at their request, or they may be withdrawn at any time at the discretion of the Sponsor, PI, or designee for safety, behavioral, or administrative reasons. If a subject does not return for a scheduled visit, at least 3 documented attempts will be made to contact the subject in order to establish the reason for withdrawal, and the outcome will be documented. The PI or designee should inquire about the reason for withdrawal, request that the subject return for a final visit, if applicable, and follow-up with the subject regarding any unresolved AEs.

When a subject withdraws from the trial and also withdraws consent for disclosure of future information, no further evaluations should be performed and no additional data should be collected. The PI and staff may retain and continue to use any data collected before such withdrawal of consent.

In case of early subject withdrawal, subjects may be replaced based upon overall enrollment numbers and with the approval of the Sponsor.

## **8. STATISTICAL ANALYSIS METHODS**

The Sponsor's Quantitative Sciences Department will be responsible for the data management and statistical analyses of this trial.

Demographic and baseline characteristics will be summarized by treatment. For continuous variables, descriptive summary will include number of subjects, mean, standard deviation, median, minimum and maximum values. For categorical variables, descriptive summary will include the number and percentage of subjects in each response category.

### **8.1. STATISTICAL ANALYSIS POPULATIONS**

██████████ efficacy data will be evaluated for all intent-to-treat (ITT) subjects who used the IP and had baseline and at least one post-baseline data point. AEs will be summarized for all subjects who signed the ICD, differentiating Pre-Treatment Adverse Events (see section 10.3.2.1).

## **8.2. EFFICACY ANALYSIS**

For each efficacy variable, summary statistics will be provided by treatment group at each time point. For continuous variables, descriptive summaries will include number of subjects, mean, standard deviation, median, minimum and maximum values. Distributions of categorical variables will be summarized by presenting the number and percent of subjects in each response category.

### **8.2.1. Analysis of Primary Variable**

The primary efficacy variable is the change from baseline in global wrinkling at Week 12. Scores from the 3 Expert Graders will be averaged for the baseline readings as well as the Week 12 readings before computing the change. For each subject, the change from baseline is then computed by subtracting post-baseline mean global wrinkling from baseline mean global wrinkling. The mean change from baseline for each cell will be presented together with a two-sided 95% confidence interval. Superiority to baseline will be concluded if the upper bound of the 95% confidence interval for the mean difference is below -0.5. The active mask will be compared with the sham mask. Treatment means and between-treatment differences will be assessed by means of an ANCOVA model with treatment and skin type group as factors and the corresponding averaged baseline score as a covariate. The two-sided 95% confidence interval for the treatment difference will be presented. Analysis of the primary efficacy variable will be based on the average scores as well separately for the scores from each Expert Grader.

If global wrinkling is missing at Week 12 for more than 5% of the subjects, the missing value will be imputed by using the last observation carried forward (LOCF) method.

### **8.2.2. Analysis of Secondary Variables**

The secondary efficacy variables are the change from baseline in the following endpoints at Week 1, Week 4, Week 12, and Week 24. Scores from the 3 Expert Graders will be averaged for the baseline as well as each post-baseline visit before computing the change.

- Global wrinkling (excluding Week 12, the primary time point)
- Fine lines
- Periorbital wrinkles
- Surface roughness
- Uneven skin tone
- Mottled hyperpigmentation
- Sallowness or yellowing
- Lack of radiance

The active mask will be compared with the sham mask. Treatment means and between-treatment differences will be assessed by means of an ANCOVA model with treatment and skin type group as factors and the corresponding averaged baseline score as a covariate. The two-sided 95% confidence interval for the treatment difference will be presented.

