## 5. SAMPLE SIZE

A sufficient number of subjects will be screened to enroll up to approximately 125 subjects in order to finish with at least 96 subjects (targeting 48 subjects per cell). Enrollment will be evenly distributed across all Fitzpatrick skin types (i.e. an approximately equal number of subjects will be enrolled per skin type per cell, targeting 8 subjects per Fitzpatrick skin type per cell to complete the study).

Refer to section 8.4 for the sample size determination rationale.

If the final overall sample size is smaller than expected (i.e. less than 96 subjects complete the study), a protocol deviation should be recorded and communicated to the Sponsor.

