5 HANDLING OF MISSING VALUES

If global wrinkling is missing at Week 12 for more than 5% of the subjects, the missing value will be imputed by using the last observation carried forward (LOCF) method.

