6.4.2 Primary Analysis

The primary efficacy variable is the change from baseline in global wrinkling at Week 12. Scores from the 3 Expert Graders will be averaged for the baseline readings as well as the Week 12 readings before computing the change. For each subject, the change from baseline is then computed by subtracting post-baseline mean global wrinkling from baseline mean global wrinkling. The mean change from baseline for each cell will be presented together with a two-sided 95% confidence interval.

The active mask will be compared with the sham mask. Treatment means and between-treatment differences will be assessed by means of an ANCOVA model with treatment and skin type group as factors and the corresponding averaged baseline score as a covariate. The two-sided 95% confidence interval for the treatment difference will be presented. Analysis of the primary efficacy variable will be based on the average scores as well separately for the scores from each Expert Grader.

For the secondary efficacy variables, scores from the 3 Expert Graders will be averaged for the baseline as well as each post-baseline visit before computing the change. The analyses of the secondary efficacy variables will be based on average scores and will be performed as for the primary efficacy variable.

The tertiary efficacy variable is the change from baseline at Week 1, Week 4, Week 12, and Week 24 for [REDACTED]

[REDACTED]

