7 SIGNATURES PAGE

APPENDIX 1 SUMMARY OF EFFICACY ANALYSES

Endpoint	Analysis Set	Statistical Method	Model/ Covariates	Missing Data
Mean efficacy change from Baseline	FAS	ANCOVA	Skin type group / Baseline mean	Excluded
Treatment differences in mean efficacy change from Baseline	FAS	ANCOVA	Treatment, skin type group / Baseline mean	Excluded

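### The secondary ANCOVAs discard the earlier scores of any woman who misses Week 24, which can bias that comparison and gives up some precision; one repeated-measures model per parameter would use them

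*Protocol*

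**What the plan says.** Protocol 8.2.2 defines the secondary set: "The secondary efficacy variables are the change from baseline in the following endpoints at Week 1, Week 4, Week 12, and Week 24". It lists seven parameters at all four visits, plus global wrinkling at every visit except Week 12, which is primary. The model is an "ANCOVA model with treatment and skin type group as factors and the corresponding averaged baseline score as a covariate". SAP 6.4.2 adds: "The analyses of the secondary efficacy variables will be based on average scores and will be performed as for the primary efficacy variable". Neither document specifies a visit term, a subject effect or a within-subject covariance. Separate fits at each visit are therefore an inference, but the natural one.

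On missing data, the SAP Appendix 1 row "Treatment differences in mean efficacy change from Baseline" shows missing values as excluded. The only imputation rule, in protocol 8.2.1 and SAP section 5, is last observation carried forward (LOCF). It applies on one condition: "If global wrinkling is missing at Week 12 for more than 5% of the subjects". It is written for that variable at that visit only.

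The full analysis set (protocol 8.1, SAP 3.1) admits any woman who used the product and has a baseline and at least one later value. On attrition, protocol section 5 plans to "enroll up to approximately 125 subjects in order to finish with at least 96 subjects", and protocol 7.5.2 includes "Lack of efficacy" among possible reasons for discontinuation.

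**The concern.** A woman seen at Weeks 1, 4 and 12 but not at Week 24 belongs to the analysis set yet drops out of all eight Week 24 comparisons. Her earlier scores are recorded and carry information about the missing one. The per-visit ANCOVA is free of bias only if absence is unrelated to response, given baseline and skin type group.

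Week 24 is where this matters most. Loss accumulates up to the last visit, and it is the only visit that addresses the off-treatment part of the objective. If women who improved least leave more often, and the mask works, more of them leave from the sham cell. The sham women who remain then look better than the full cell would, and the difference shrinks toward zero. If absence is unrelated to response there is no bias, but usable information is still discarded.

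**Working it through.** **Inputs from the documents.** Up to about 125 enrolled, at least 96 finishing, 48 per cell, treatment effect 0.7, two-sided alpha 0.05, power 92% (protocol sections 5 and 8.4).

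**Assumed, because the documents do not give them.** SD 1; between-visit correlation 0.3 to 0.7; true difference 0.7 at Week 12 and 0.5 at Week 24; the dropout mechanism.

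**1. Number of comparisons.** 7 × 4 + 3 = 31, of which 8 are at Week 24.

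**2. The plan's own power figure.** Power = Φ(δ/√(2/n) − 1.96) with SD 1. With n = 48 and δ = 0.7: √(2/48) = 0.204; 0.7/0.204 − 1.96 = 1.47; Φ = 92.9%. The noncentral t gives 92.4%. The stated 92% is reproduced if 0.7 is in SD units, which is why SD 1 is used below.

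**3. Ceiling on loss.** (125 − 96)/125 = 29/125 = 23.2%.

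**4. Precision when loss is random.** Let d be the fraction lost between Weeks 12 and 24, and r the baseline-adjusted correlation of those two visits. Effective n per cell is n(1 − d) under exclusion and n/[(1 − r²)/(1 − d) + r²] under a likelihood repeated-measures model. With n = 62.5 and d = 0.232, exclusion leaves 62.5 × 0.768 = 48.0. For r = 0.7 the model gives 62.5/(0.51/0.768 + 0.49) = 62.5/1.154 = 54.2.

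| r | Effective n: exclusion | Effective n: model | Power at 0.5: exclusion | Power at 0.5: model |
|---|---|---|---|---|
| 0.3 | 48.0 | 49.0 | 68.8% | 69.7% |
| 0.5 | 48.0 | 51.0 | 68.8% | 71.4% |
| 0.7 | 48.0 | 54.2 | 68.8% | 74.0% |

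With d = 0.10, exclusion leaves 56.25 per cell, and power at 0.5 goes from 75.5% to between 75.9% (r = 0.3) and 77.6% (r = 0.7). Placing all the loss after Week 12 is the case most favourable to the model.

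**5. Bias and power by simulation.** There were 4,000 trials per scenario, with 62 and 63 women, four visits, and dropout without return. The log-odds of dropout depended on improvement at the previous visit, by the same rule in both cells. The correlation was either constant across visits or decaying with distance. The excluded-case Week 24 difference was compared with the maximum-likelihood estimate by sequential regression, which is equivalent to an unstructured repeated-measures model under this missingness pattern. Baseline and skin type were treated as already adjusted for.

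At about 77% seen at Week 24:

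- Dropout unrelated to response: bias about 0 for both methods; the model gains about 0 to 6 points of power.
- Dropout odds doubling or tripling per SD of poorer response: exclusion is biased by about −0.01 to −0.06 points, the likelihood estimate by no more than 0.01; the model gains about 2 to 13 points.

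At 10% loss with response-related dropout, the bias is about −0.01 and the gain about 2 to 3 points in the middle of the assumed range. A separate large-sample check, with a true difference of 0.35, correlation 0.3 to 0.8 and its own same-rule dropout mechanism, gave −0.02 to −0.03 at 10% loss.

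**6. Scale.** The Week 24 standard error is about 0.20, so the largest bias in step 5 is about 0.06/0.20 = 0.3 standard errors.

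**The case against.** The best counter-argument is that nothing in the documents shows that bias will occur. They give no dropout rate or pattern by cell. Lack of efficacy is one entry in a generic list of possible reasons, and no mask is used between Weeks 12 and 24, so efficacy-driven exit in that interval is not obvious. Different dropout rates in the two cells, if unrelated to response, produced a bias of about 0. All of this stands, and it is why the point says exclusion can bias Week 24, not that it does.

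The effect is also small: below the half-point grading step, and toward zero under the same-rule mechanism, so there it would not manufacture a benefit. The secondary endpoints carry no success criterion. These facts limit the importance of the point without removing it.

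The simulation favours the model by construction, because dropout depends only on observed scores. That is fair. If absence depends on the unseen Week 24 score itself, neither method is protected.

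Finally, the protocol synopsis and SAP 6.4.2 say the secondary variables are analysed like the primary, which could be read as extending LOCF to them. The rule's own wording and SAP Appendix 1 point the other way. Extending it would also carry an end-of-treatment score across 12 weeks without the mask, hiding the regression that Week 24 is there to measure.

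**Conclusion.** The plan leaves recorded earlier scores unused in the secondary comparisons, and a better analysis is available at almost no cost. With SD 1, correlation 0.3 to 0.7, a Week 24 difference of 0.5 and loss at the 23% ceiling, exclusion costs about 0 to 6 points of power if dropout is random. If dropout odds double or triple per SD of poorer response, it costs 2 to 13 points and brings a bias of about −0.01 to −0.06. At 10% loss the effects are clearly smaller. Every one of these figures rests on assumed values.

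A reader might infer three stronger things, none of which the documents support:

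- That Week 24 is biased. Bias requires response-related loss, and nothing shows that it will occur. Much larger values arise if poor responders leave only the sham cell (−0.07 to −0.17 at 23.2% loss, against a true difference of 0.35 and correlation 0.3 to 0.8), but no passage indicates such a pattern.
- That 23% dropout is planned. It is the gap between an approximate upper limit and a minimum, and protocol 7.5.2 allows withdrawn women to be replaced.
- That the stated 92% power is undermined. It is already based on 96 completers and concerns the wrinkle scale. No power is claimed for any secondary endpoint.

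**What to change.** For each secondary parameter, make the main analysis one likelihood-based repeated-measures model on the full analysis set: change at Weeks 1, 4, 12 and 24, with treatment-by-visit, baseline-by-visit and skin type group as fixed effects and an unstructured within-woman covariance. From it, report the active-minus-sham difference and the within-cell mean changes at each visit, with 95% confidence intervals. Keep the per-visit ANCOVA as a supportive table.

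For global wrinkling the model also yields a Week 12 estimate. State that the Week 12 conclusion comes only from the pre-specified primary analysis and that the model's Week 12 estimate is supportive. Amend protocol 8.2.2, SAP 6.4.2 and the SAP Appendix 1 missing-data entry for the secondary endpoints to match.

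The cost is SAP wording and a modest amount of programming, with no new data, visits or subjects. The small downside is reliance on a missing-at-random assumption, but that is weaker than what exclusion needs, because it also conditions on the scores already collected.

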### 8.2.3. Analysis of Tertiary Variables

[REDACTED]

[REDACTED]

[REDACTED]

### 8.3. [REDACTED] Safety Analysis

[REDACTED]

The safety analysis will be based on all randomized subjects who use IP. The number and percentage of subjects experiencing AEs during the clinical study will be presented by MedDRA System Organ Class, preferred term, and treatment. A listing of AEs will be provided for all subjects who signed the ICD, differentiating Pre-Treatment Adverse Events.

### 8.4. SAMPLE SIZE DETERMINATION

The total sample size of 96 (48 per treatment cell) completed subjects provides 92% power to detect a treatment effect of 0.7 using a two-sided test at the 0.05 significance level. The 0.7 effect size is estimated based on a previous study of similar design using the 9-point Fitzpatrick Wrinkle and Elastosis Scale.

[REDACTED]

[REDACTED]

## 10. MANAGEMENT OF INTERCURRENT EVENTS

### 10.1. AMENDMENTS TO THE PROTOCOL

Neither the PI/Site nor the Sponsor will modify this protocol without obtaining the agreement of the other.

Amendments must be approved by the Sponsor and the IRB/IEC prior to implementation.

Note that submission of administrative change/non-substantial amendments to regulatory authorities and/or IRB/IECs for approval prior to study implementation is determined after consultation with the local regulatory representative and/or IRB/IEC policy and may vary by country/region.

The only circumstance in which an amendment may be initiated prior to IRB/IEC approval is where the change is necessary to eliminate apparent immediate hazards to the subjects. In that event, the PI must notify the IRB/IEC and the Sponsor in writing within 3 working days after the implementation.

